11.1 Demographics

Baseline demographics will be summarized by treatment arm and overall, for all participants in the ITT.

Baseline demographic data to be evaluated will include age at screening (years), age categories (18 to <55 years, 55 to <60 years, 60 to <65 years, 65 to <70 years, 70 to <75 years, >=75 years) sex, race, ethnicity, region, as well as the baseline values of height (cm), weight (kg), body mass index (BMI) [kg/m²], and body surface area (BSA) [m²]. In addition, use of tobacco (status, pack-years smoked, years smoked, <10 pack years, >=10 pack years), alcohol (status, average of alcohol units per week, rehabilitation or treatment program needs), or any substance use rehabilitation or treatment program will be summarized.

Supporting participant data listing for demographic characteristics will be provided.

Specifications for computation:

- BSA $[m^2] = 0.007184 * (Baseline weight (kg)^0.425)* (Baseline height (cm)^0.725)$
- BMI $\lceil kg/m^2 \rceil$ = Baseline weight $(kg) / \lceil (Baseline height (cm)/100)^2 \rceil$

11.2 Medical and Surgical History

Medical and surgical history will be coded using the last available version of Medical Dictionary for Regulatory Activities (MedDRA).

Medical and surgical history will be summarized by treatment arm and overall, for all participants in the ITT set.

Summary of medical and surgical history will include number and percentage of participants with a medical/surgical history condition overall, per System Organ Class (SOC) and per Preferred

Term (PT) within each SOC. A participant contributes only once to the count for a given medical/surgical history (SOC or PT). Medical and surgical history will be sorted by descending overall incidence in SOC and PT. In case of the same incidence, alphabetical order of SOC and PT will be applied.

Participant data listing will include condition/procedure, start and end dates, any treatment for condition and NCI-CTCAE grade (if ongoing).

11.3 Other Baseline Characteristics

Information on disease characteristics collected at baseline will be summarized overall and by treatment arm based on ITT. Summary statistics will be presented for:

- ECOG performance status: 0, 1, 2, 3 and 4.
- Feeding tube in place
- Primary tumor localization: larynx, hypopharynx and oropharynx (from eCRF), and larynx versus other (from Integrated Randomization Technology [IRT]).
- Time since initial diagnosis (months).
- AJCC cancer staging: III,IVa, IVb.
- Tumor size: T0, T1, T2, T3, T4a, and T4b (from eCRF), and T4 versus other (from IRT);
- Tumor grade: Gx, G1, G2, G3, G4, and Not Done
- Lymph node involvement: N0, N1, N2a, N2b, N2c and N3 (from eCRF), and N0-1 versus N2 versus N3 (from IRT);
- Metastasis: M0, M1.
- Number of target lesions: 1,2 3, ...
- Number of nodal target lesions: 1, 2, 3, ...
- Number of non-nodal target lesions: 1, 2, 3, ...
- Number of non-target lesions: 1,2 3, ...
- Sum of diameter of measurable disease at screening (mm).

Supporting participant data listing for baseline cancer characteristics will be provided.

Specifications for computation:

• Time since initial diagnosis (months) = (date of randomization - date of initial diagnosis) / 365.25 * 12.

12 Prior, Concomitant and Subsequent Medications/Procedures

Medications will be classified into 3 categories:

- Prior, defined as medications started before the first dose date regardless if continued at the time of starting study intervention.
- Concomitant, defined as medications taken any time during the on-treatment period.
- Subsequent, defined as medications started after the on-treatment period.

If the start and/or end date of a prior, concomitant, and subsequent medication is missing, it will be imputed as specified in Section 9.12.1.

The last available version of the World Health Organization Drug dictionary (WHO-DD) will be used for coding of medications.

Prior and concomitant medication as well as subsequent antineoplastic therapies will be summarized by treatment arm and overall, for all participants in the ITT set.

Prior and concomitant medication and subsequent antineoplastic therapies, each will be summarized by number and percentage of participants overall, per Anatomical Therapeutic Chemical (ATC) Classification level 2 and per preferred term within each ATC level 2. A participant contributes only once to the count for a given medication (ATC level 2 or preferred term). Medications will be sorted by descending overall incidence in ATC level 2 and preferred term. In case of equal incidence, alphabetical order of ATC level 2 or preferred term will be applied. In addition, subsequent antineoplastic therapies will be summarized by treatment arm and overall, according to types that are mapped by medical review.

In addition to medications, the surgical procedures summary will include the number and percentage of participants with a surgery, type of surgery, planned surgery, hospitalization, radical salvage surgery and pathological complete response together with the summary of anatomopathological findings (% viable cells) by treatment arm and overall, for the ITT set.

Prior and concomitant medication as well as subsequent antineoplastic therapies will be listed. Concomitant procedures, if any, will also be listed.

12.1 Concomitant 5-HT3 Receptor Antagonist

Concomitant 5-HT3 receptor antagonist medications (any medication coded with ATC Level 4 equal to "SEROTONIN (5HT3) ANTAGONISTS") will be summarized overall and by treatment arm for all participants from SAF set who reported renal toxicity (grade 3 or 4) vs. participants who did not report renal toxicity. Renal toxicity grade 3 or 4 includes any participant with at least one post-baseline toxicity grade 3 or 4 for estimated Glomerular Filtration Rate (eGFR) or Creatinine. The following will be summarized:

• Number and percentage of patients with any 5-HT3 receptor antagonist medication.

- Number and percentage of patients by 5-HT3 receptor antagonist medication alone. PT will be used to summarize each medication.
- Number and percentage of patients with any combination of 5-HT3 receptor antagonist medications.

Supportive listings will be provided for patients with and without renal toxicity (grade 3 or 4) who took concomitant 5-HT3 receptor antagonist medication.

13 Study Intervention: Compliance and Exposure

The exposure to xevinapant/matched placebo, cisplatin/carboplatin, and IMRT will be summarized by cycle and overall, by actual treatment arm for all participants from SAF set. The following extent of exposure parameters will be summarized:

- Number of treatment cycles, defined as the number of cycles in the eCRF with non-zero dose administration of xevinapant/matched placebo, cisplatin/carboplatin. No cycle is defined for IMRT.
- Treatment duration (in weeks) is calculated per study intervention component as
 - \circ Chemotherapy treatment duration = (last dose date first dose date + 21)/7 weeks
 - Cisplatin treatment duration = (last dose date first dose date + 21)/7 weeks
 - Carboplatin treatment duration = (last dose date first dose date + 21)/7
 weeks
 - \circ IMRT treatment duration = (last dose date first dose date + 3)/7 weeks

Xevinapant / Placebo treatment duration = (last dose date - first dose date + 8)/7
 weeks

Overall treatment duration is defined as the maximum of xevinapant / placebo treatment duration, chemotherapy treatment duration, and RT treatment duration.

- Total cumulative dose, per treatment (units' treatment specific), calculated as the sum of the dose in mg/m² for cisplatin and in Gy for IMRT administered during the treatment duration. The total cumulative dose for cisplatin will also be summarized into categories <100 mg/m², 100 to <200 mg/m², 200 to <300 mg/m², >=300 mg/m². The total cumulative dose for IMRT will also be categorized into <50, 50-<70, >=70 Gy.
- Dose intensity of xevinapant/matched placebo (mg/day) is defined as the total dose of xevinapant/matched placebo taken during a cycle, divided by the cycle duration in days. Overall dose intensity is calculated as the mean of the dose intensities of the individual cycles.
- Relative dose intensity of xevinapant/matched placebo, expressed in %, for any defined period is calculated as the dose intensity for that period divided by the planned dose intensity for that period * 100, where the planned dose intensity equals 2800/21 mg per day. Relative dose intensity will also be categorized into <80%, 80%-<100%, 100%. Additionally, the relative dose intensity will be computed during the combination period (first 3 treatment cycles only) and separately during the monotherapy period (cycles 4-6) and will be categorized into <80, 80%-<100%, 100%.
- Dose intensity of cisplatin in mg/m²/week is defined as the total dose of cisplatin (mg/m²) taken during a cycle, divided by the cycle duration in days and multiplied by 7. Overall dose intensity is derived as the mean of the dose intensities of the individual cycles.
- Dose intensity of carboplatin in mg·min/mL/week is defined as the total dose of carboplatin (mg·min/mL) taken during a cycle, divided by the cycle duration in days and multiplied by 7. Overall dose intensity is derived as the mean of the dose intensities of the individual cycles.
- Relative dose intensity of cisplatin/carboplatin, expressed in %, is calculated as the dose (mg/m² or mg·min/mL, respectively) received divided by the planned dose *100, where the planned dose equals 100 mg/m² per cycle for cisplatin and 5 mg·min/mL per cycle for carboplatin.
- Time to first dose reduction (days), defined as the date of the first dose to the date of the first dose reduction, or the date of the first dose interruption if participants had a dose interruption followed by a dose reduction.
- Number of participants receiving cisplatin or carboplatin at a specific cycle.

• For participants receiving cisplatin, the number and percentage of participants with preinfusion hydration and post-infusion administered at a specific cycle.

In addition, for each cycle the number and percentage of participants who had missed, interrupted, reduced, or discontinued doses, together with the reason(s) will be summarized for each treatment component (xevinapant/matched placebo, and cisplatin/carboplatin). Additionally, the switch to carboplatin per participant will be presented for each cycle. For each modification action, each distinct reason will be reported in each specific category.

Supportive participant data listings will be presented.

14 Efficacy Analyses

The efficacy analyses will be performed based on the ITT set by treatment arm, except when otherwise stated.

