 - History of myocardial infarction, or severe/unstable angina, within 6 months prior to randomization.
 - \circ New York Heart Association grade ≥ 3 congestive heart failure.
 - Symptomatic pulmonary disease requiring continuous or intermittent oxygen supply. Exclusion criteria 17
 - Non-compensated or symptomatic liver cirrhosis (Child-Pugh score: B or C). Exclusion criteria 21
- History of another malignancy within the last 3 years prior to randomization, with the
 exception of completely resected non-melanoma cell skin cancer outside the head and neck
 area or completely resected stage I breast cancer, or completely resected in-situ
 nonmuscular invasive bladder, cervix and/or uterine carcinomas or T1a squamous cell
 carcinoma of the esophagus. Exclusion criteria 18
- Missed baseline CT scan or MRI. Inclusion criteria 5
- Prior treatment for LA SCCHN
- Xevinapant/matched placebo relative dose intensity below 67% compared to the prescribed dose not due to a medical or safety reason
- Did not receive 200 mg/m2 or more of the overall planned cisplatin dose not due to a medical or safety reason

- Did not receive 66.5 Gy or more of the planned dose of the IMRT not due to a medical or safety reason
- Use of prohibited concomitant medication
- Any criterion identified during the Blind Data Review Meeting prior to database lock which may impact the efficacy analysis.

All protocol deviations are documented in the Study Data Tabulation Model (SDTM) domain DV. All important protocol deviations (including cIPDs) are documented in the Analysis Data Model (ADaM) domain ADDV whether identified for all participants by either medical review processes or programming, and confirmed prior to or at the Blind Data Review Meeting at the latest.

The cIPDs as well as the IPDs will be summarized by treatment arm and overall, for all participants in the ITT.

11 Demographics and Other Baseline Characteristics

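### On its natural reading, xevinapant relative dose intensity is 100% after any whole number of full-dose cycles, so the 67% deviation criterion misses non-medical stopping at a cycle end

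*SAP*

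**What the plan says.** SAP Section 13 (Study Intervention: Compliance and Exposure) builds the measure in steps. Per-cycle dose intensity is "defined as the total dose of xevinapant/matched placebo taken during a cycle, divided by the cycle duration in days". The step to the overall value reads: "Overall dose intensity is calculated as the mean of the dose intensities of the individual cycles". Relative dose intensity (RDI) "for any defined period is calculated as the dose intensity for that period divided by the planned dose intensity for that period", "where the planned dose intensity equals 2800/21 mg per day". It is reported overall, and separately for cycles 1–3 and cycles 4–6.

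The section does not say whether a planned cycle that was never started is left out of the mean or enters as zero. It also does not say how long a cycle lasts when dosing is broken off partway. The nearest guidance is the cycle count, "defined as the number of cycles in the eCRF with non-zero dose administration of xevinapant/matched placebo, cisplatin/carboplatin", and the default in SAP Section 9.12 that missing values are not imputed unless a rule says so.

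SAP Section 10.2 lists as a clinically important protocol deviation (cIPD): "Xevinapant/matched placebo relative dose intensity below 67% compared to the prescribed dose not due to a medical or safety reason". The next two items in that list set floors of 200 mg/m² for cisplatin and 66.5 Gy for IMRT, with the same restriction on reasons.

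Total cumulative dose in Section 13 is introduced as a per-treatment quantity, but is then "calculated as the sum of the dose in mg/m² for cisplatin and in Gy for IMRT"; xevinapant is not named. Protocol Table 3-1 and SAP Table 1 list actual dose and RDI among the secondary exposure endpoints for all treatment agents.

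**The concern.** RDI as defined is a rate over the cycles that have a value, divided by a constant rate. Nothing in it falls when later cycles are not given. Yet Section 10.2 uses it as a threshold for how much of the prescribed drug was received, next to two criteria that are whole-course totals.

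Three things are at stake. First, the overall RDI summary, a listed secondary exposure endpoint, does not distinguish a participant who took one full cycle from one who took six. Second, the deviation table flags some participants who took more drug and passes others who took less. Third, because the set of cycles is not stated, two programmers could report 100% or 16.7% for the same participant. The cycles 4–6 summary has the same weakness: it has no value for anyone who never starts cycle 4, so it describes only those who continued.

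**Working it through.** **Inputs.** Planned regimen: 200 mg/day on Days 1–14 of a 21-day cycle, 6 cycles (Protocol 6.1.2.1). Planned rate: 2800/21 mg/day (SAP 13). Threshold: RDI below 67% (SAP 10.2).

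**The plan's own figure.** 200 × 14 = 2,800 mg per cycle; 2,800/21 = 133.33 mg/day. This reproduces the SAP's planned rate. Planned course: 6 × 2,800 = 16,800 mg; each three-cycle period: 8,400 mg.

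**Stopping at the end of a cycle, full dose throughout.** With the mean taken over cycles with dosing, RDI = 100 × [(c × 133.33)/c] / 133.33 = 100% for every c. Percent of planned course = 100 × c/6.

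| Full cycles taken | RDI, cycles with dosing | Percent of 16,800 mg |
|---|---|---|
| 1 | 100% | 16.7% |
| 2 | 100% | 33.3% |
| 3 | 100% | 50.0% |
| 4 | 100% | 66.7% |
| 5 | 100% | 83.3% |

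**Stopping partway through a cycle.** After c full cycles and k further dosing days, with the broken-off cycle counted as 21 days, RDI = 100 × (c + k/14)/(c + 1).

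- Cycle 1 only: k = 9 gives 64.3%, k = 10 gives 71.4%. Flagged for 9 or fewer days.
- One full cycle, then cycle 2: k = 1 gives (1 + 1/14)/2 = 53.6%, k = 4 gives 64.3%, k = 5 gives 67.9%. Flagged for 1 to 4 days.
- Two full cycles, then cycle 3: the lowest value is (2 + 1/14)/3 = 69.0%. Never flagged. The minimum is higher still with more full cycles.

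**Sensitivity to the undefined duration.** SAP 13 computes xevinapant treatment duration as last dose minus first dose plus 8 days. Applied to the broken-off cycle, this gives k + 7 days and a cycle value of 1.5k/(k + 7) of the planned rate. Flagging then shrinks to 5 or fewer days in cycle 1 (62.5% at 5 days, 69.2% at 6) and 1 or 2 days in cycle 2 (59.4% and 66.7%; 72.5% at 3 days). After two full cycles the minimum is 72.9%.

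**Non-monotonicity.** With 21-day cycles, 2,800 mg scores 100% and is not flagged; 3,000 mg (one full cycle plus one day) scores 53.6% and is flagged. Against the planned course these are 16.7% and 17.9%.

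**Neighbouring criteria.** Cisplatin: 200/300 mg/m² = 66.7% of three planned doses of 100 mg/m². IMRT: 66.5/70 Gy = 95.0%. Both are totals over the whole course.

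**The case against.** The strongest reply is that the SAP never says unstarted cycles are excluded. The non-zero-dose wording defines a different quantity, the number of cycles. The cIPD item refers to the prescribed dose, and its neighbours are whole-course totals, so the sponsor may intend the full course; one cycle would then be 16.7% and flagged. This stands to the extent that the started-cycles reading is an inference. It remains the natural one, because a cycle without a duration cannot be averaged, no zero rule is given, and the denominator is a rate. If the full course was intended, the Section 13 formula does not deliver it.

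A reader might also infer that the 67% rule cannot detect early stopping, or that RDI stays near 100% however many participants stop. Neither is supported: breaking off early within cycle 1 or 2 can fall below 67%, and missed days and dose reductions lower RDI. Nor do the documents say that 67% was chosen as four cycles of six.

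It is also fair to say that early stopping is reported elsewhere: cycle counts, treatment duration and per-cycle discontinuations with reasons (SAP 13), disposition by reason (SAP 10.1.2), and TEAEs leading to discontinuation (SAP 15.1.2). Treatment non-compliance is already an important deviation, the cIPD list is not exhaustive, and the blinded data review may add criteria. Some non-medical stopping, such as withdrawal of consent, is provided for in Protocol 7.1 and need not be a deviation. All of this limits the consequence, but none of it makes the RDI threshold behave sensibly.

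**Conclusion.** The point holds in a limited form. With RDI averaged over cycles with dosing, full-dose stopping after 1 to 5 complete cycles always scores 100%, against 16.7% to 83.3% of the planned course. The 67% criterion misses non-medical stopping at the end of a cycle and every full-dose stop after two or more full cycles, and it can flag a participant who took more drug than one it passes.

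This rests on the natural but unstated reading of which cycles enter the mean. The size of the non-monotonicity and the exact flagging limits also depend on the length assumed for a broken-off cycle; that no full-dose stop after two full cycles is flagged holds under both lengths tried.

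The effect is confined to the exposure summary and the deviation table. Efficacy is analysed in the ITT set, the SAP defines no per-protocol set, and cIPDs are only summarised. A reader might infer that early stopping would go unseen in the report or that efficacy results are at risk; the documents support neither. The change is worth making because the defect is clear and the remedy is cheap.

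**What to change.** In SAP Section 13:

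- Add total cumulative xevinapant/placebo dose.
- Add percent of planned course dose = total taken / 16,800 mg, with 8,400 mg for each three-cycle period and unstarted cycles contributing zero.
- Keep the per-cycle RDI as a separate on-treatment delivery-rate summary. State that it covers cycles with dosing, and define the duration of a truncated cycle.

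In SAP Section 10.2, base the 67% criterion on percent of planned course dose and keep the restriction to non-medical, non-safety reasons. State whether exactly four full cycles is meant to be flagged: 4 × 2,800 = 11,200 mg is 66.7%, just under 0.67 × 16,800 = 11,256 mg, whereas a participant with exactly 200 mg/m² of cisplatin is not flagged.

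The cost is SAP wording and one extra derived variable, with possibly more flagged deviations. No new data collection is needed beyond the dosing records already used for dose intensity.

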In the Debio 1143-201B Phase 2 study, up to 3 cycles of high-dose cisplatin were safely administered concomitantly with standard fractionated IMRT and xevinapant. The median cisplatin dose delivered was equivalent and high in both arms (288 mg/m²). Significantly improved antitumoral activity was observed in the xevinapant + CRT arm over the placebo + CRT arm (Section 2.3.2). Therefore, the same high-dose cisplatin regimen will be used in the present study in combination with xevinapant and as the comparator arm.

Nevertheless, in the current study, participants who will experience decreased estimated glomerular filtration rate (eGFR) (< 60 mL/min/1.73m² using the Chronic Kidney Disease - Epidemiology Collaboration [CKD -EPI] creatinine formula) after the first cisplatin dosing, can be switched to an equivalent carboplatin doses (area under the concentration vs time curve [AUC] 5.0 Q3W). This regimen is widely accepted and was reported to have similar efficacy in a recent study (Wilkins et al. 2013).

IMRT

The anatomy of the head and neck is complex due to multiple elements of the digestive, respiratory, nervous and endocrine systems located sometimes within millimeters of each other. Due to the complexity of this anatomical region, large and multiple target volumes, and proximity to organs at risk, RT in this region is also complex.

In addition, high-dose fractionated RT (60-72 Gy) is necessary to cure patients. Irradiation of critical normal tissue can cause severe discomfort with increased acute and late morbidity (Marta et al. 2014). Newer techniques have been developed over the past 2 decades to improve delivery of RT with 2 aims. Firstly, to avoid critical normal tissue to decrease toxicity (Jellema et al. 2007). Secondly, to administer a dose to the tumor volume high enough in order not to compromise control rates (Ghosh-Laskar et al. 2016). Techniques were therefore developed to shape the radiation beams more closely to the target volumes to spare critical tissues, hence reducing toxicity.

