6.1.2.2. Chemotherapy

All participants will receive high-dose cisplatin (100 mg/m²) intravenously over at least 90 minutes on Day 2 Q3W up to a maximum of 3 cycles in total (see administration schedule in Table 1-1 and Table 1-2). If body surface area is >2.00 m², total administered dose will be capped at a maximum of 200 mg. Please consult and follow cisplatin administration instructions provided in your local label. The infusion has to be administered with pre- and post-infusion hydration +/- mannitol and/or diuretics, according to institutional guidelines. Any pre-existing dehydration should be corrected. Please refer to Appendices 13.2 and 13.3 for additional information on cisplatin administration and suggested hydration regimen.

eGFR (using the CKD-EPI creatinine formula) should be ≥60 mL/min/1.73m² before administration of cisplatin at C1D2; re-treatment conditions as specified in Table 6-1 should be met.

Participants should receive at least one dose of cisplatin on C1D2.

Standard antiemetic prophylaxis for high-dose cisplatin containing regimens are mandatory starting on Day 1 of each chemotherapy containing cycle. Standard antiemetics guidelines (administration of pre- and post-treatment 5-HT3 receptor antagonists, neurokinin-1 receptor antagonists and dexamethasone [or any other corticosteroid at equivalent dose i.v.] according to the 2016 MASCC and ESMO guideline (Roila et al. 2016)]) are provided in Section 6.5.1; however the specifics of the regimen are at the discretion of the treating physician, provided adequate control is achieved.

Note: Dose and schedule of dexamethasone coupled with its wide availability in various forms established it as the agent of choice in the 2016 MASCC and ESMO guideline. If an equivalent dose of corticosteroids is used according to institutional guidelines, the risk of increased toxicity to corticosteroids should be carefully monitored. Elevations of plasma levels may be triggered by xevinapant inhibition of CYP3A4.

The participant can switch to carboplatin in C2 and/or C3 as per the dose modifications outlined in Table 6-1 (NCCN Chemotherapy Order Templates 2020). Please consult and follow the carboplatin administration instructions provided in your local label.

No pre- or post-treatment hydration or forced diuresis is required for carboplatin administration.

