6.1.2.2.1. Dose Modification, Interruption and Discontinuation of Chemotherapy

Permitted cisplatin dose levels:

- Planned dose (level 0): corresponds to cisplatin 100 mg/m²
- Dose level -1: corresponds to cisplatin 75 mg/m² (-25% from prior dose level: capped at 150 mg total dose)
- Dose level -2: corresponds to cisplatin 50 mg/m² (-25% from prior dose level: capped at 100 mg total dose)

For participants switching to carboplatin: carboplatin AUC = 5 mg·min/mL or AUC = 4 mg·min/mL is allowed.

Please refer to Table 6-1 for instructions on dose modifications, interruption, and discontinuation of chemotherapy in case of toxicity suspected to be related to study treatment.

Toxicity related to chemotherapy administration includes but is not limited to nausea, vomiting, renal toxicity (with an elevation of blood urea nitrogen and creatinine and impairment of endogenous creatinine clearance, as well as renal tubular damage, which appears to be transient), peripheral neuropathy, ototoxicity (with hearing loss that initially is in the high-frequency range, as well as tinnitus) and hyperuricemia. Much more severe and prolonged toxicity has been observed in participants with abnormal or obstructed urinary excretory tracts. Myelosuppression, often with delayed anemia is expected.

Chemotherapy dose adjustments at the start of a cycle should be based on the nadir of hematologic counts or maximum non-hematologic toxicity from the previous treatment cycle. chemotherapy infusion may be delayed to allow for sufficient recovery time.

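### SAP Section 13 measures cisplatin exposure against an uncapped 100 mg/m², so a participant with BSA above 2.00 m² who receives every full protocol dose is reported below 100% and below the top cumulative class

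*SAP*

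**What the plan says.** Protocol Section 6.1.2.2 gives cisplatin at 100 mg/m² "on Day 2 Q3W up to a maximum of 3 cycles in total" and sets a ceiling: "If body surface area is >2.00 m², total administered dose will be capped at a maximum of 200 mg". Section 6.1.2.2.1 carries the ceiling to the reduced levels. Level -1 "corresponds to cisplatin 75 mg/m² (-25% from prior dose level: capped at 150 mg total dose"; level -2, 50 mg/m², is capped at 100 mg.

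SAP Section 13 does not mention the ceiling. Cisplatin RDI is the mg/m² received divided by the planned dose, "where the planned dose equals 100 mg/m² per cycle for cisplatin". Total cumulative dose is "calculated as the sum of the dose in mg/m² for cisplatin and in Gy for IMRT administered during the treatment duration", and the two highest reporting classes are "200 to <300 mg/m², >=300 mg/m²".

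SAP Section 10.2 lists this among the clinically important protocol deviations (cIPDs): "Did not receive 200 mg/m2 or more of the overall planned cisplatin dose not due to a medical or safety reason". In the same list the xevinapant criterion is relative: an RDI below 67% of the prescribed dose.

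Actual dose, dose intensity and relative dose intensity of chemotherapy are secondary endpoints (Protocol Table 3-1, SAP Table 1).

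**The concern.** Above 2.00 m² the protocol itself plans less than 100 mg/m² per cycle, so the SAP's denominator is not the protocol's plan. A participant treated exactly as the protocol directs then appears to have a shortfall, and the shortfall grows with body size. The fixed 300 and 200 mg/m² thresholds have the same basis.

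These tables are the evidence on whether the chemoradiotherapy backbone was delivered. Protocol Section 2.3.1 allows that xevinapant may make chemoradiotherapy toxicity more frequent and more severe. Section 4.3 relies on delivered mg/m² from Phase 2: "The median cisplatin dose delivered was equivalent and high in both arms (288 mg/m²". A reader will use the Phase 3 figures in the same way, so they should separate a capped dose from a reduced or omitted one.

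**Working it through.** **Inputs.** 100 mg/m² per cycle, at most 3 cycles, and the 200 mg cap (Protocol 6.1.2.2); 150 mg and 100 mg caps at the reduced levels (Protocol 6.1.2.2.1); RDI denominator of 100 mg/m² and the cumulative classes (SAP 13); cIPD threshold of 200 mg/m² (SAP 10.2); BSA = 0.007184 × W^0.425 × H^0.725 (SAP 11.1). The BSA values below are illustrative, because the documents give no BSA distribution.

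**The protocol's own figures reproduce.** At BSA 2.00 m², 100 × 2.00 = 200 mg, 75 × 2.00 = 150 mg and 50 × 2.00 = 100 mg. All three caps correspond to a BSA of 2.00 m².

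**Formulas**, taking mg/m² received as administered mg divided by BSA:
- administered mg per cycle = min(100 × BSA, 200)
- SAP RDI = (administered mg / BSA) / 100
- cumulative dose = number of full doses × administered mg / BSA

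| BSA (m²) | mg per full dose | SAP RDI | 3 full doses (mg/m²) | 2 full doses (mg/m²) |
|---|---|---|---|---|
| 1.80 | 180 | 100% | 300 | 200 |
| 2.00 | 200 | 100% | 300 | 200 |
| 2.01 | 200 | 99.5% | 298.5 | 199.0 |
| 2.10 | 200 | 95.2% | 285.7 | 190.5 |
| 2.20 | 200 | 90.9% | 272.7 | 181.8 |
| 2.40 | 200 | 83.3% | 250.0 | 166.7 |
| 2.50 | 200 | 80.0% | 240.0 | 160.0 |

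**RDI and classes.** Every row above 2.00 m² is full protocol dosing. Every one has RDI below 100% and falls in the 200 to <300 class. By the SAP's formula, 2.00 m² is reached at 88.6 kg for a height of 170 cm, 80.3 kg at 180 cm and 73.3 kg at 190 cm.

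**Reduced levels.** At level -1 and BSA 2.20 m², 150 / 2.20 = 68.2 mg/m², reported as 68.2%. A participant at or below 2.00 m² on the same level is reported as 75%.

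**cIPD threshold, three full doses.** 600 / BSA < 200 requires BSA > 3.00 m², about 209 kg at 180 cm or 190 kg at 190 cm. In practice these participants are not flagged.

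**cIPD threshold, two full doses.** 400 / BSA < 200 for every BSA above 2.00 m², while at or below 2.00 m² the total is exactly 200 and is not flagged. If the third dose was missed for a non-medical reason, the larger participant is a cIPD and the smaller one, also with two full doses, is not. As a fraction of the protocol plan the threshold is 200 / (600 / BSA) = BSA / 3 above 2.00 m²: 73% at 2.20 and 80% at 2.40, against 200 / 300 = 67% at or below 2.00.

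**After the correction.** With planned dose per cycle = min(100 × BSA, 200) mg, a full dose above 2.00 m² gives 200 / 200 = 100% at any BSA, level -1 gives 150 / 200 = 75%, and two of three full doses give 67%.

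**The case against.** The strongest objection is that the result depends on how the case report form holds the dose. Protocol Section 6.1.2.2.1 names dose levels in mg/m² and writes the cap into the reduced levels. SAP Section 13 takes carboplatin in mg·min/mL, the unit of its nominal AUC levels. If cisplatin is recorded as the nominal level, a capped full dose scores 100% and the discrepancies disappear. That reading is possible, but neither document states it, and Section 13 speaks of dose administered and received. Nominal recording would also leave the cumulative summary overstating delivery: 300 mg/m² reported at BSA 2.20 when 273 was given. A definition is needed on either reading.

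A second objection is that 286 mg/m² at BSA 2.1 is a true statement of exposure per m². That stands, and is why the mg/m² summary should stay. It does not justify the RDI, which claims to compare with the plan.

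A third is that little follows from the error. The cap is the same in both arms of a blinded randomized trial. The SAP has no per-protocol set, cIPDs are only summarized in the ITT set after confirmation at or before the blind data review, and SAP Section 13 puts RDI into categories only for xevinapant. All of this stands and limits the point to descriptive reporting.

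Stronger readings that a reader might infer, and that the documents do not support:
- That large participants who receive all three doses become cIPDs, or that the cIPD table will hold false deviations. The first needs BSA above 3.00 m². In the two-dose case a planned dose really was missed; the fault is unequal classification.
- That cisplatin delays go unseen because the RDI has no time term. SAP Section 13 separately reports cisplatin intensity in mg/m²/week from actual cycle length. A full uncapped dose in a 27-day cycle shows there as 21/27 = 78% of the planned 33.3 mg/m²/week. With the other two cycles at 21 days, the overall mean is (1 + 1 + 0.778)/3 = 93% of that plan.
- That the comparison between arms or the efficacy results are biased. Nothing in the plan links the cap to treatment or to the ITT analyses.

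**Conclusion.** The point holds as a mismatch between the SAP's exposure definitions and the protocol's cap. Provided mg/m² received is administered milligrams divided by BSA, full protocol dosing above 2.00 m² is reported as RDI below 100% (95% at 2.1, 91% at 2.2, 83% at 2.4) and can never enter the top cumulative class. The cIPD threshold is uneven by body size at exactly two full doses with a non-medical miss of the third. The SAP also does not say whether a shortfall caused only by the cap counts as a medical or safety reason.

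A secondary exposure endpoint is therefore given a wrong value by a stated rule. The consequences stay within the exposure, compliance and deviation tables and should be similar in both arms. How many participants are affected cannot be derived from the documents. The passages need to be reconciled; no view is taken on the dosing rule itself.

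**What to change.** In SAP Section 13:
- State that mg/m² received is administered milligrams divided by BSA, and whether that is baseline BSA (the only one defined, in Section 11.1) or BSA at each cycle.
- Define planned cisplatin per cycle in line with the protocol's existing cap, as the smaller of 100 mg/m² × BSA and 200 mg, and compute RDI against it.
- Express the cumulative categories as a percentage of the participant's protocol-planned dose, and keep the mg/m² summary as descriptive.

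In SAP Section 10.2, express the cisplatin cIPD cut-off as a percentage of the same planned dose, as the xevinapant criterion already does, and say how a shortfall due only to the cap is classified.

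Optionally, put cisplatin RDI on the same time basis as xevinapant RDI, or relabel it as relative dose, so that one term does not carry two meanings in one section.

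The cost is SAP wording and programming, assuming the dosing form records milligrams given. Percentage categories compare less directly with other chemoradiotherapy trials, which showing both summaries resolves.
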